# 4.2.1 Participant Input into Design

Not applicable.

# 4.3 End of Study Definition

A participant is considered to have completed the study after he/she has completed blood collection and is discharged from the collection location, even if not all the study tubes are collected.

The end of the study is defined as the date of the analysis of the samples collected from the last participant in the study.

# **5 STUDY POPULATION**

#### Natural Sample Group

Participants will be recruited

in-person, via phone, or via electronic communications, such as social media, using IRB-approved recruitment materials. In order to cover the assay measurable range (AMR) additional in- and out- patient hospital populations with disease states such as the below listed conditions may be enrolled.

- Part A: Patients with hepatic, renal, endocrine, cardiovascular disorders and/or cancer.
- Part B: Patients with hematological disorders, cancers, diabetes and/or allergies.

Page 26 of 67

-- Protocol |

Protocol Number: Version: 4.0 Date: 07 September 2022

Approximately equal number of female and male participants with a targeted enrollment of at least 30% of either gender

. The patient disease state and gender will be documented on a CRF.

# **Contrived Sample Group**

Participants enrolled for the preparation of contrived samples

# 5.1 Inclusion Criteria

### **Natural Sample Group**

In order to be eligible to participate in this study, an individual must meet all of the following criteria:

- 1. Participants  $\geq 18$  years of age.
- 2. Not currently pregnant (self-reported)
- 3. Adequate access to four fingers and inner elbows for blood collection procedures
- 4. Willing and able to comply with all study procedures and evaluations
- 5. Ability to read, write, and understand English language
- 6. Provision of signed and dated informed consent form

# **Contrived Sample Group**

Participants enrolled for the preparation of contrived samples must meet the criteria laid out within the **second second**. Participants who have been enrolled within **second** have already been screened according to the inclusion criteria for that program.

# 5.2 Exclusion Criteria

#### **Natural Sample Group**

Participants are excluded from the study if any of the following criteria apply:

- 1. Evidence of skin issues such as infections, ulcerations, blisters, peripheral vascular disease, inflammation, extensive scarring or calluses, or healed burns at the site.
- 2. Subject to post-study exclusion period for this or other related studies:
  - a. A study participant may enroll once in study part A and once in study part B of this clinical study. They may not enroll more than once in a single study part.
  - b. If a study participant has previously enrolled in one study part and would like to enroll in the second study part, they must wait from the time of the first study part collection procedures to enroll in the second study part collection procedures.

-- Protocol |

Protocol Number: Version: 4.0 Date: 07 September 2022

3. Any condition which, in the opinion of the Investigator, would preclude participation in this study.

### **Contrived Sample Group**

Participants enrolled for the preparation of contrived samples must meet the criteria

### 5.3 Lifestyle Considerations

There are no required lifestyle considerations or restrictions.

#### 5.4 Screen Failures

Screen failures are defined as participants who do not meet all eligibility criteria. Individuals who do not meet the criteria for participation in this study (screen failure) may not be rescreened.

#### **6 STUDY INTERVENTIONS**

#### 6.1 Investigational/Test Device

	Protocol	
Protoc Versic Date:	col Number: on: 4.0 07 September 2022	CONFIDENTIAL
6.2	Comparator Devices/Standard of Care	
	Part A	SST), 400-600 µl,
	
 
• [T05] SST™ Blood Collection Tube (
 
	SST),
	
 
[T06] Blood Collection Tube with Clot Separator
 
	t Activator and Gel valent.
	Part B	
	
 
EDTA), or equivalent.
 
[T09]
 
	EDTA).
	• [T10]	22,
	EDTA),	
6.3	Ancillary Devices/Products	
	•	

### 6.4 Device Labeling

Investigational devices (or the immediate packaging) shall be labeled in accordance with regulatory requirements, including the following statement: "For Investigational Use Only". The performance characteristics of this product have not been established."

The devices used during current venipuncture collection practices and capillary blood specimen collections are all commercially available and will be labeled as provided by the manufacturer.

For contrived samples blood will be collected from participants

#### 6.5 Measures to Minimize Bias

#### 6.5.1 Randomization

All randomization schedules are to be provided by BD

#### Natural Sample Group

Collection method (venous vs. capillary), tube collection order (within collection method),

location	will be randomized according
to a draw schedule.	

#### **Contrived Sample Group**

For the contrived samples, indirect draw order will be randomized according to a draw schedule. Tube testing order on instrument will be randomized according to a test schedule.

#### 6.5.2 Blinding/Masking

Not applicable, this is an open-label study.

#### 7 STUDY PROCEDURES AND ASSESSMENTS

- Study procedures, assessments for natural samples and their timing are illustrated in the respective schemas provided in Section 1.2. Protocol waivers or exemptions are not allowed.
- Adherence to the study design requirements is essential and required for study conduct.
- Procedures conducted as part of the participant's routine clinical management (e.g., blood count) and obtained before signing of the ICF may be utilized for screening or baseline purposes provided the procedures met the protocol-specified criteria.
- The Instructions for Use (IFU) is a reference document for the investigational Test Device product; this study protocol will supersede the Test Device IFU.

Page 30 of 67

7.2

#### 7.1 Screening, Informed Consent, and Enrollment

Potential study participants will be screened against the inclusion and exclusion criteria outlined in Section 5. Participants will first be asked to provide written informed consent. Those who provide consent will be considered enrolled and will be assigned a unique participant number. Those meeting eligibility criteria will receive information regarding the study, including but not limited to test procedures, information to be collected, number and type of blood collection procedures, potential risks and benefits, and other pertinent information.

Part A	
Natural Sample Group:	
Contrived Sample Group:	
Part B	
Natural Sample Group:	
Contrived Sample Group:	
Blood Collection Procedure	
Natural Sample Group	
Study Part A:	one veninuneture using e
collect blood into a	tube. The collection
will be performed per the study site's	standard operating procedure for venipuncture. In
addition,	collections using
	. A

the Test Device system. The collection end time for each conventional and Test Device capillary tube collected from a participant will be noted on the CRF. For venous collections, the collection end time will be the time of the last tube collected from a venipuncture draw. Duration of collection for all capillary collections (conventional and Test Device) will also be captured

on CRFs as described in section 7.7 of this protocol, Supplemental Measurements, Visual Observations, and Analyte Testing. Study Samples will be mixed and processed per their respective IFUs.

Study Part B: For each participant,	one venipuncture
to collect blood into a	
tube. The collection will be performed per the study site's standard	ard operating procedure for
venipuncture. In addition, one one	e (1) conventional capillary
collection	tube.
	collection using the
Test Device EDTA	system. The collection end
time for each conventional	and Test Device
tube collected from a participant will be noted on the CRF. F	For venous collections, the
collection end time will be the time of the last tube collected	from a venipuncture draw.
Duration of collection for all capillary collections (conventional	and Test Device) will also
be captured on CRFs as described in the supplemental measurem	nents section section 7.7 of
this protocol, Supplemental Measurements, Visual Observations	, and Analyte Testing.

### **Contrived Sample Group**

An overview of the spiking approach for the preparation of contrived samples is outlined in Appendix B. If multiple sets of contrived specimens are prepared from a single participant, each unique set of contrived samples will be assigned a unique pool number.

# 7.3 Test Device Blood Collection Procedure

#### Natural Sample Group

Page 33 of 67

#### Step 9: Apply Gauze

• Apply the sterile gauze or pad to the puncture site. Direct the patient to hold and apply pressure if they are able to assist.

The collection end time for each conventional and Test Device tube collected from a participant will be noted on the CRF. For venous collections, the collection end time will be the time of the last tube collected from a venipuncture draw

#### **Contrived Sample Group**

The procedures for the collection of blood for the preparation of the contrived samples are outlined in the overview of the spiking approach in Appendix B.

Once the contrived samples are indirectly transferred into the study tubes, they will be processed in the same manner as the natural samples.

# 7.4 Repeat Collection

In cases of insufficient sample volume or loss of sample during collection, repeat collection may be needed. Repeat collection will vary based on blood collection method. Participants should be asked for their permission before attempting a repeat collection.

#### Natural Sample Group Part A: SERUM

Capillary Collections – A total of four capillary collections will be performed

**Venipuncture** -1 additional venipuncture will be allowed, for a total of 2 venipunctures for Part A of this study.

# Part B: EDTA

Capillary Collections – A total of two capillary collections will be performed

**Venipuncture:** 1 additional venipuncture will be allowed, for a total of 2 venipunctures for Part B of this study.

# **Contrived Sample Group**

Repeat collections on participants enrolled for the preparation of contrived samples

Page 36 of 67

# 7.5 Participant Compensation

Participants will be compensated for their time and participation after the study procedures are complete.

# 7.6 Natural and Contrived Sample Storage and Processing

Page 37 of 67

# Part A: SERUM

After tube inversions, all Serum tubes need to stand for their minimum clot times and then centrifuged as indicated in Table 1.

. All tubes from the same participant	
will be centrifuged within the same timeframe.	Remove
samples from centrifuge as soon as centrifugation is completed.	

For Natural samples, all tubes from the same participant will be processed and tested at the same timeframe using the same lot of reagents. For contrived samples, all tubes from the same pool set will be processed and tested at the same timeframe using the same lot of reagents.

# Part B: EDTA

Complete tube inversions as indicated in Table 1 for all EDTA tubes.

All tubes from the same participant will be processed and tested at the same timeframe using the same lot of reagents. Place Test Device container into adapter for automated processing on the instrument.

Table 1: Tube Processing

Tube				Centrifuga	tion †
Number	Tube type	Inversions*	Minimum Clot Time	Time	G-force (g)
T01, T02					
T03, T04		5	45 min	90 sec	6500
Т05		5	30 min	10 min	1300
T06		5	30 min	10 min	1800
T07			N/A	N/A	N/A
T08		8	N/A	N/A	N/A
Т09		8-10	N/A	N/A	N/A
T10		8-10	N/A	N/A	N/A

†All serum tubes will be centrifuged within 2 hours of their respective collection end time. All tubes from the same participant (Natural Sample Group) or from the same contrived sample pool will be centrifuged within the same timeframe

\*Mix blood with additives in the tubes immediately after collection using the indicated number of tube inversions

# 7.7 Supplemental Measurements, Visual Observations, and Analyte Testing

• Duration of collection (applicable to only Natural Samples): Defined as time in seconds between puncture timestamp and additive/blood mix start timestamp per

- Protocol |

Protocol Number: Version: 4.0 Date: 07 September 2022

tube type. This parameter will only be collected for tubes T01-T04, Capillary collections.

- Volume of Serum (applicable to only Natural Samples):
- Plasma, Free Hemoglobin (applicable to Natural and Contrived Samples): As measured on Siemens Atellica.

The following visual observations will be assessed during part A for Natural Samples. For Contrived Samples all visual observations in Table 2 also apply with the exception of the visual observation for collection failure.

Table 2: Visual Observations for Part A

Visual Observation	Rating	Description	Ideal Rating	Note
Complete Fill	1, 2, (3)		2	Performed after collection, right before mix start timestamp
Collection Failure	0, 1, 2, 3, 4		0	

Page 40 of 67

Downloaded on 31 Oct 2023 System Version Number 1.0 -- Protocol |

CONFIDENTIAL

Protocol Number: Version: 4.0 Date: 07 September 2022

Fibrin mass (distinct from fibrin strands)	0, 1, 2, 3	0	Performed as soon as possible after centrifugation and prior to testing
Fibrin strands (distinct from fibrin masses)	Y/N	N	
Gel Barrier formation	0, I, C	С	
Red blood cells on barrier	0, 1, 2, 3	0	
Hemolysis	0, 1, 2, 3	0	references takes)

# 7.7.1 Part A: SERUM (Natural and Contrived Samples)

Serum samples from the Test Device and comparator tubes will be tested ('analysis time') on the Siemens Atellica platform after centrifugation as noted in Table 3 and within 4 hours from the collection end time. For the contrived samples the full panel of analytes may not be run on each contrived sample set. The specific analytes to be tested for each contrived sample set will be detailed in the Spiking Plan. Analysis time is defined as the

-- Protocol |

Protocol Number: Version: 4.0 Date: 07 September 2022

> time at which the sample is aspirated by the instrument. All serum samples from the same subject will be tested within the same timeframe using the same lot of reagents. Test Device SST tubes should be to enable serum sampling from the primary tube. The primary tube is may be aliquoted into sample cups prior to analysis.

Table 3: Analytes to	be Measured in	Part A Natural and	Contrived Samples
----------------------	----------------	--------------------	--------------------------

Analytes	Abbreviation					
Immunoassays						
Thyroid-Stimulating Hormone	TSH					
Vitamin D	Vit D					
Enzyme	-					
Alkaline Phosphatase	ALP					
Alanine Aminotransferase	ALT					
Aspartate Aminotransferase	AST					
Lipid						
High-Density Lipoprotein	HDL					
Low-Density Lipoprotein	LDL					
Total Cholesterol	CHOL					
Triglycerides	TRIG					
Metabolic						
Albumin	ALB					
Total Bilirubin	TBIL					
Blood Urea Nitrogen	BUN					
Calcium	Ca					
Carbon Dioxide	CO2					
Chloride	Cl					

Page 42 of 67

- Protocol |

CONFIDENTIAL

Protocol Number: Version: 4.0 Date: 07 September 2022

Creatinine	CRE	
Glucose	GLU	
Potassium	K	
Sodium	Na	
Total Protein	ТР	

By default, TSH will be measured in capillary tubes T01 **and the same and T03 and T03 and T04 and T0** 

# 7.7.2 Part B: EDTA

Supplemental Measurements:

- Duration of collection (applicable to only Natural Samples):
   This parameter will only be collected for for for for for and T08.
- Volume of Whole Blood (applicable to only Natural Samples):
- Smear Reviews: (applicable to Natural and Contrived Samples) Peripheral smears will be reviewed in response to applicable instrument flags. Details on smear reviews provided below.

The following visual observations will be assessed during part B for Natural Samples. For Contrived Samples only the visual observation of complete fill will be assessed.

Table 4: Visual Observations for Part I	Table 4:	4: Visua	Observations	for	Part	B
---	----------	----------	---------------------	-----	------	---

Visual Observation	Rating	Description	Ideal Rating	Note
Complete Fill	1, 2, (3)		2	Performed after collection, right before mix start timestamp

volume

Testing to be done in Part B includes the following whole blood parameters and instrument platforms (Table 5). EDTA samples from the Test Device EDTA and comparator tubes will be tested ('analysis time') within 4 hours from collection end time. For the contrived samples the full panel of analytes may not be run on each pooled set. The specific analytes to be tested for each pooled set will be detailed in the Spiking Plan. Analysis time is defined as the time at which the sample is aspirated by the instrument (instrument print out time). All tubes from the same participant will be processed at the same timeframe using the same lot of reagents. Test Device EDTA tubes will be performed at room temperature.

Table 5: Ana	lvtes to be r	neasured in	Part B Natural	and Contrived	Samples
	-,				

Analytes	Abbreviation	Instrument
Basophils (%)	BA	Sysmex XN 1000
Eosinophils (%)	EO	

Erythrocyte Count	RBC	
Hematocrit	Hct	
Hemoglobin	Hgb	
Leukocyte Count	WBC	
Lymphocytes (%)	LY	
Mean Corpuscular Hemoglobin	МСН	
Mean Corpuscular Hemoglobin Concentration	МСНС	
Mean Corpuscular Volume	MCV	
Monocytes (%)	МО	
Neutrophils (%)	NE	
Platelet Count	PLT	
Red Cell Distribution Width (RDW-SD / RDW- CV)	RDW-SD / RDW-CV	
Instrument flags	N/A	
Hemoglobin A1c	HbA1c	Bio-Rad D-100

Relevant instrument flags will be confirmed with manual blood smears. Blood smears will be prepared on all tubes with instrument flags (asterisks and IP messages), as appropriate. For platelet flags, 10 high power fields on the smear will be scanned for platelet clumps and rated according to the below criteria.

Pro	tocol
Protocol Number: Version: 4.0 Date: 07 September 2022	CONFIDENTIAL
Moderate	
Marked	

# 7.8 Natural and Contrived Sample Acceptance and Rejection Criteria for Analyte Testing

Part A: Samples with the following visual scores will be rejected:

- Complete Fill
- Collection failure
- Gel Barrier
- Visual Hemolysis

Part B: Samples with the following visual scores will be rejected:

- Complete Fill
- Collection failure

# 7.9 Repeat Testing Natural and Contrived Samples

For study part A and B, repeat analyte testing is to occur on a per analyte basis following analyzer test run errors or flags during testing of the analyte, as deemed appropriate by the laboratory staff per their procedures. Repeat analyte testing should occur within the prescribed test window for each study part (within 4 hours of collection for Part A, and within 4 hours of collection for Part B).

If upon the first run, a valid test result is not obtained due to any test run error or no numerical value is obtained, a repeat test should be run, volume permitting. Both the original and repeat test result will be provided and clearly marked.

For Part B, if a network instrument flag is noted on the test report, a smear will be prepared and reviewed. Check the sample for the following and repeat the test on the network is a smear will be prepared and reviewed.

- 1. Adequate sample volume
- 2. Mix sample well, (observe for any "hang-up" in sample tube- smaller tubes need more time with the inversions to mix well)
- 3. Check sample integrity no clots within sample or on tube top

The first valid result will be used for analysis. If both the first and repeat run is flagged by an asterisk, this data point should be documented with the asterisk in the study database and the first result with the asterisk will be used in the analysis.

Page 46 of 67

-- Protocol

Protocol Number: Version: 4.0 Date: 07 September 2022

# 7.10 Residual Sample Usage (Natural Sample Group Only)

After study objectives are met, samples of After study objectives are met, samples of sufficient quantity to collect data supporting the use of the Test Device for analysis of additional analytes. 

Page 47 of 67

-- Protocol |

Protocol Number: Version: 4.0 Date: 07 September 2022

	a arrant of realizations at the
In th	e event of voluntary study
participant withdrawal, bio-banked samples will be destroyed	per the study participant
request	

# **Contrived Sample Group**

This section is not applicable to contrived samples. Contrived samples will be disposed of according to standard laboratory procedures after the completion of the clinical study testing.

# 7.11 Safety Evaluations

# **Natural Sample Group**

Adverse events will be actively collected while the participant is at the site and collected via self-report through telephone calls over 7 days after blood collection.

# **Contrived Sample Group**

Safety Evaluations are outlined in document

# 8 PARTICIPANT DISCONTINUATION/WITHDRAWAL

# 8.1 Discontinuation/Withdrawal

Page 48 of 67

# Natural Sample Group

- A participant may withdraw from the study at any time at his/her own request or may be withdrawn at any time at the discretion of the investigator or sponsor for safety, behavioral, compliance, or administrative reasons. This is expected to be uncommon.
- At the time of discontinuing from the study, no further study assessments will be performed. Adverse events that occur and are self-reported by the participant to the PI and study staff will be documented for up to 7 days after discontinuation from the study.
- If the participant withdraws consent for disclosure of future information, the sponsor may retain and continue to use any data collected before such a withdrawal of consent.
- If a participant withdraws from the study, he/she may request destruction of any samples taken and not tested, and the investigator must document this in the site study records.

#### **Contrived Sample Group**

Safety Evaluations are outlined in document

#### 8.2 Lost to Follow-Up

Not applicable, study will be completed in one visit.

### 9 ADVERSE EVENTS AND DEVICE DEFICIENCIES

#### 9.1 Definitions of Events

#### 9.1.1 Adverse Events (AEs)

An adverse event is defined as any untoward medical occurrence, inappropriate patient management decision, unintended disease or injury, or untoward clinical signs in participants, users, or other persons, with any connection to study related activities, whether or not related to the IVD medical device under investigation (ISO 20916). In this study, participant AEs are limited to those occurring immediately before, during, and immediately after specimen collection. Also, based on the nature of the study, test results will not be used for patient management decisions.

For the purpose of this study, Adverse events will be collected by the study team from enrollment through completion of the study (once discharged). If an adverse event occurs during this time the PI is required to follow-up with the participant. The clinical course of the event will be followed according to accepted standards of medical practice until the event resolves, stabilizes, or in the opinion of the Investigator, is no longer considered clinically significant. The Investigator must document the adverse event outcome on the AE CRF through a follow-up call to the participant.

Page 49 of 67

-- Protocol |

Protocol Number: Version: 4.0 Date: 07 September 2022

The participant may self-report any additional AEs that occur through 7 days post discontinuation by calling the site.

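### Section 9.1.1 limits participant adverse events to the moments around collection, which contradicts the 7-day self-report period and could leave delayed related events out of the safety summary

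*Combined protocol and SAP*

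**What the plan says.** Section 9.1.1 begins with a broad definition of an adverse event taken from ISO 20916. It then narrows that definition for this study: "participant AEs are limited to those occurring immediately before, during, and immediately after specimen collection". The section goes on to have the study team collect events from enrollment until discharge, and it closes with: "The participant may self-report any additional AEs that occur through 7 days post discontinuation by calling the site".

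Two other sections use a 7-day period, both under the Natural Sample Group:

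- Section 7.11 has events gathered actively during the visit and then "collected via self-report through telephone calls over 7 days after blood collection".
- Section 8.1, for participants who discontinue, says that self-reported events "will be documented for up to 7 days after discontinuation from the study".

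Safety is a stated objective in section 3, and its endpoint is device- or procedure-related AEs. Sections 10.3 and 10.5.3 promise a summary of all such events in all enrolled participants. Neither gives a time window. For the Contrived Sample Group, section 7.11 says only that "Safety Evaluations are outlined in document" and points elsewhere, so this point concerns the Natural Sample Group.

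**The concern.** A definition decides what is recorded and counted, so a restrictive sentence inside it carries weight. If participant AEs stop immediately after collection, an event that appears on one of the following days is not an AE, even though the same section invites the participant to report it as one.

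The events at stake are ones that the protocol foresees. The risk table in section 2.2.1 lists infection for both venipuncture and capillary collection, and bruising or hematoma for venipuncture. These can become apparent after the participant has gone home. Two sites, or a site and an analyst, could each follow the protocol and classify the same event differently. The safety summary would then depend on which sentence was applied.

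**Working it through.** No arithmetic applies. The check sets the provisions side by side and follows one illustrative event through them: a finger puncture-site infection that a Natural Sample participant notices on day 3 and reports by telephone.

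1. **Limiting sentence, section 9.1.1.** Day 3 is not immediately after collection. Read literally, the infection is not a participant AE.
2. **Last sentence, section 9.1.1.** Day 3 lies within the 7 days, and the sentence calls such events additional AEs. The infection is an AE.
3. **Section 7.11.** Day 3 lies within 7 days of blood collection. The infection is collected as an AE.
4. **Section 8.1.** If the participant had discontinued, the infection would be documented in the same way.
5. **Study-team collection until discharge, section 9.1.1.** This fits steps 2 to 4: staff collect until discharge, and self-report follows. Only step 1 does not fit.
6. **Sections 10.3 and 10.5.3.** The summary counts related AEs and sets no window. It neither excludes the day-3 infection nor settles the conflict between step 1 and steps 2 to 4.

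The next question is whether other definitions would catch the event if step 1 were applied.

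- **Section 9.1.3 (adverse device effects).** The first sentence requires an adverse event. The second extends the definition to any event arising from malfunction, inadequate instructions or user error, with no time limit. A delayed infection with one of those causes is covered. One without such a cause depends on the AE definition.
- **Section 9.3 (relatedness).** The upper categories ask whether timing after device use was reasonable or plausible. They do not require the event to be immediate, which supports counting delayed events.
- **Section 9.1.4, with one-working-day reporting in section 9.4.** Unanticipated device effects and unanticipated serious problems are covered. For capillary collection, the risk table attributes the infection risk to the instructions for use and package insert, so an ordinary infection of that kind would normally count as anticipated and not be caught here.

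The remaining exposure is therefore mainly delayed events that are non-serious or anticipated.

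The start of the 7 days also varies: blood collection in section 7.11, discontinuation in sections 8.1 and 9.1.1. Section 4.3 treats a participant as complete "after he/she has completed blood collection and is discharged from the collection location", and section 8.2 reads "Not applicable, study will be completed in one visit". In a one-visit study these starts will usually fall on the same day, so this difference is minor.

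**The case against.** The strongest reply is that the surrounding text already settles the matter. The section containing the limiting sentence ends by calling the 7-day events AEs. Section 7.11 collects them, and sections 10.3 and 10.5.3 promise all related events without a time limit. Section 9.1.3 reaches beyond the limiting sentence for malfunction, inadequate instructions and user error, section 9.3 judges timing by reasonableness, and section 9.6 records device deficiencies separately. Section 10 says that the SAP will be finalized before database lock with more detail, so a counting rule may yet appear there. The protocol also describes the risk as minimal.

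Much of this stands. A reader might infer that the plan drops delayed events from the safety summary. The documents do not support that, because most of the text points the other way. A reader might also infer that every delayed event falls out of the device-effect and serious-event definitions. Sections 9.1.3 and 9.1.4 prevent that for many device effects. Section 9.1.2 defines serious events by reference to outside standards, so the documents alone do not show that it inherits the limit.

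What the reply does not remove is the sentence itself. It is an explicit restriction in the definitions section, and no other provision says that it yields. A later SAP rule could settle what is counted, but it could not recover an event that a site, relying on the definition, never recorded as an AE.

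**Conclusion.** The contradiction is real and should be corrected. It is an inconsistency in wording with a conditional consequence: if the limiting sentence is applied as written, a delayed device- or procedure-related event in the Natural Sample Group can be left out of the safety summary; if the 7-day text is applied, it is counted.

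The size cannot be stated as a number. The documents give no expected frequency of delayed events, and sections 10.3 and 10.5.3 promise a summary, not a rate. The disputed period runs from just after collection to day 7. The conclusion assumes only that some foreseen events, such as infection, can first appear in that period. Equivalence results are not affected.

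A reader might also see a material conflict over when the 7 days begin, or over who telephones whom. Neither amounts to much. The starting points nearly coincide in a one-visit study, and sections 7.11 and 9.1.1 both describe self-report by telephone and read naturally together.

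**What to change.** Remove the limiting sentence in section 9.1.1, or reword it so that it agrees with the 7-day period already stated for the Natural Sample Group: events collected by the study team up to discharge, plus events that participants self-report within the 7 days. State in sections 10.3 and 10.5.3, or in the SAP, that device- or procedure-related AEs reported within that period count in the safety summary. The starting point of the 7 days can be aligned across sections 7.11, 8.1 and 9.1.1 in the same edit, so that it also fits participants who complete the study.

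The change is to wording only. It introduces no new follow-up period, because the 7 days are already in the protocol. The cost is a few more AEs to record and summarize.
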